Objectives	
In ten patients undergoing DBS implantation for PD, we will implant a subdural cortical electrode in addition to the DBS electrode, and connect these to a novel implantable pulse generator that can store / stream field potential data (Medtronic Activa PC+S, Medtronic Summit RC+S). At multiple time points post-implantation up to 5 years, in our clinic or patients' homes, cortical and subcortical signals will be recorded. Data will be collected while patients are resting or engaged in emotion/cognition tasks and while cortical stimulation on and off. In addition to brain signals recordings, symptoms will be assessed using validated questionnaires and tasks to allow identification of neurophysiological correlates of non-motor symptoms. These signals will be used to determine the optimal stimulation parameters to disrupt symptom-related neural activity, and to implement feedback-controlled cortical stimulation
 
Hypotheses:
 
 
1) Characteristics of the prefrontal ECoG potentials (spectral power in specific bands, interaction between different frequency bands and/or between brain regions) correlate with severity of non-motor symptoms
 

	
2) For patients who have non-motor fluctuations in mood, anxiety, or impulsivity in response to dopaminergic medication, characteristics of the prefrontal ECoG potentials will vary in relation to medication state.
 
3) Cortical stimulation can reduce the severity of non-motor symptoms
 
4) Patients can learn how to voluntarily modulate cortical signals related to non-motor symptoms

Patient Population	Study subjects will be adults with Parkinson's disease (PD) deemed appropriate candidates for the treatment of motor symptoms using deep brain stimulation. Study subjects will also have one or more of the following non-motor symptoms: depression, anxiety, or impulsive behavior.
Sample Size	10 subjects

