16-17	At least 12 month after implantation	Research: blind test of the effect of cortical stimulation on non-motor symptoms.	Stimulation: Cortical on and off Medication: regular medication	-Physiological signals - Symptom assessments
18-19	13 to 24 months after implantation (every 6 months +/- 20 days)	Clinical: Follow-up at 18 months, motor and non-motor symptoms evaluation at 24 months  Research: Download data collected daily over the last month; Train subjects to voluntarily modulate their pathological brain signals using computer-based tasks.	Stimulation: off  Medication: on	-Rest -Symptom evaluation
20-21	3 to 5 years after implantation (+/- 2 months)	Clinical: Follow-up at 3 to 5 years after surgery, motor and non-motor symptoms evaluation  Research: Record brain signals at rest	Stimulation: On  Medication: On	Rest -Symptom assessments
Study Visit	Time	Purpose	Therapeutic Conditions	Behavioral Conditions
Pre-surgery		Clinical: Evaluation of motor and neuropsychiatric symptoms	Stimulation: NA	-Behavioral tasks

	Within 90 days prior to surgery	Research: Informed consent; ensure eligibility; Patient will perform computer-based tasks that engaged emotion and cognition	Medication: off then on	-Symptom evaluation
1 (START OF PHASE I)	Day of surgery	Clinical: DBS Implantation and CT scan	Stimulation: DBS off  Medication: surgical anesthesia	-Rest  -Symptom evaluation
		Research: Record brain signal during surgery; evaluate the severity of anxiety and depression; verification of electrodes placement		
2	1 day after implantation, prior to hospital discharge	Clinical: postoperative follow up	Stimulation: DBS off  Medication: off and on	-Rest and behavioral tasks  -Symptom evaluation
		Research: Record brain signals with and without dopaminergic medication in order to study the effect of antiparkinsonian medication on brain signals and patient's symptoms		
3	10 days after implantation (+/- 5 days)	Clinical: Staple removal and wound check	Stimulation: DBS off  Medication: off and on	-Rest and behavioral tasks  -Symptom evaluation
		Research: Record brain signals with and without dopaminergic medication in order to study the effect of antiparkinsonian medication on brain signals and patient's symptoms		

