Once stimulation settings potentially beneficial at improving non-motor symptoms without inducing side effect have been identified, patients might be offered to participate in a blind study of the effect of chronic cortical stimulation. This 2-week clinical trial of sham versus active cortical stimulation is done in a blinded fashion in order to prevent experimental biases arising from a participants' expectations. Two stimulation conditions, active and sham, will be activated for 1h each day for 14 days in a pseudorandom fashion, while assessing symptoms with momentary questionnaires and recording brain signals. These 2 modes will be programmed in the Activa PC+S, in which up to 4 groups with different stimulation settings can be set. The 'active' mode will be set with the stimulation settings proven to be potentially therapeutic in clinic while the other ('sham') will be set with the cortical stimulation at 0V or 0mA. Every morning, for 2 weeks, participant will be asked to activate one of these 2 groups for 1h in a pseudorandom fashion, using the patient programmer. After 1h, non-motor symptoms will be assessed with tablet-based VAS and/or performance of tablet-based cognitive/emotion tasks. In addition, brain signals will be simultaneously recorded, downloaded at a subsequent visit and analyze off-line to determine the effect of stimulation on the biomarker identified in the early phase of this study. During this test, patient and the researchers interacting with the patient, will be blinded of the stimulation condition. In both group STN/GPi stimulation will be kept on and patient will be on regular PD medication to avoid potential confounding effect of DBS/medication control on motor signs. For safety, patient will be instructed to stop this test and go back to their clinical stimulation settings (with their patient programmer) if any side effects were to happen. However, our preliminary data show that chronic stimulation ( $\geq 24$ h) did not induce side effects. A similar protocol will then be used to determine whether adaptive cortical stimulation can better control mood symptoms than continuous cortical stimulation.

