Closed-loop stimulation will test a strategy for automated control of DBS settings using the aberrant neuronal signal underlying non-motor symptoms identified in phase 1 to trigger stimulation. To test stimulation strategies, at the start of a session in phase 2, Activa PC+S brain data will be collected while the patient is experiencing non-motor and/or behavioral symptoms. These data will be streamed using the Nexus-D System in conjunction with software from the Nexus-D programming interface. The Nexus System provides a conduit between Activa PC+S and a computer and can transfer stimulation update commands to Activa PC+S. Nexus data streaming will occur while the patient is seated at rest. During the streaming procedure, stimulation settings may be automatically, iteratively, adjusted based on biomarkers of non-motor symptoms. These adjustments will always remain within allowable settings pre-programmed by a clinician using standard procedures (i.e. using the Medtronic 8840 programmer). In addition, some closed loop algorithms may be implemented within PC+S without the need to stream data to an external computer using Nexus-E. The identification of non-motor symptom biomarkers will inform development of a closed-loop stimulation paradigm. The final algorithm can be uploaded on to the PC+S device using Nexus E. This allows for automated, biomarker detection-based stimulation that is completely functioning within the patient, without the need to stream to an external computer.

In addition, Nexus-D and E will be used to train subjects to voluntarily modulate the abnormal activity, in a manner that may improve these symptoms. Operant control of motor cortical oscillatory activity has been demonstrated in normal nonhuman primates (21). The Nexus-D and E will be used to represent the amplitude of the abnormal signal in the one dimensional position of a cursor on a computer screen in front of the patient. Subjects will be asked to voluntarily minimize the aberrant signals as represented by the cursor, while their non-motor symptoms are assessed.

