## **9.0 Statistical Methods and Data Analysis**

LFP data will be analyzed using wide power-spectral analysis as well as analysis of specific frequency domains (i.e. in the delta, theta, alpha, beta, gamma bands). We will also examine region-specific coherence and cross-frequency coupling in addition to coherence between cortical and subcortical brain areas. Using a repeated measures ANOVA statistical analysis, summary statistics for power in relevant frequency bands, power changes, and magnitude of coupling and coherence will be compared at different time points, different DBS conditions (on and off), different medication states (on and off), in a repeated measures (within subjects) design. The small number of subjects is mitigated by the ability to study varying mood states longitudinally within each subject. We will assess the correlation between the severity of non-motor symptoms and brain physiology measures. Additionally, bootstrapping statistical applications (i.e. a Monte Carlo algorithm) and general linear mixed models can be utilized to investigate potential statistical effects, given the small sample size).

Since this is a pilot study of chronic cortical recording, the sample size is likely to be too small to provide definitive answers to all research questions. Based on this exploratory analysis, it is anticipated that the next phase of the study will focus on a subset of the research aims, with 10 subjects per group.

Sample size calculation: This is a pilot study of a novel chronic brain recording technique. The goals are to assess technique feasibility, to collect pilot data that will be used to frame more detailed hypothesis about DBS mechanisms, and (in the add-on study using Nexus-D and E) to explore potential strategies for therapeutic use of the Activa PC+S and Summit RC+S neural interface. Thus, there is no formal sample size calculation.

*Criteria for study success that would justify a larger subsequent trial:* This study will be considered to justify a larger subsequent trial if we can demonstrate:

- 1) Chronic LFP recording from the cortex, of adequate quality to assess signatures of non-motor symptoms
- 2) No permanent serious adverse events occur
- 3) Therapeutic benefit in non-motor symptoms produced by cortical stimulation (open loop or closed loop) or neurofeedback training.

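### Neurofeedback has no designated or matched comparison condition, so neither voluntary control of the signal nor symptom benefit can be attributed to it

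*Combined protocol and SAP*

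**What the plan says.** Hypothesis 4 in the Synopsis reads: "Patients can learn how to voluntarily modulate cortical signals related to non-motor symptoms". It gives no comparator, threshold or definition of learning.

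The procedure is described briefly in section 3.0 and in section 6.0 (Nexus-D and E System Study). The amplitude of the abnormal signal drives the one-dimensional position of a cursor, and the instruction is: "Subjects will be asked to voluntarily minimize the aberrant signals as represented by the cursor, while their non-motor symptoms are assessed". Table 2 places the activity at visits 18-19, with stimulation off and medication on: "Train subjects to voluntarily modulate their pathological brain signals using computer-based tasks". The behavioural conditions listed there are rest and symptom evaluation.

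Section 6.0 (behavioural states) says that each recording session includes data at rest and during computer-controlled tasks.

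Sham and blinding appear once in section 6.0, for stimulation: "This 2-week clinical trial of sham versus active cortical stimulation is done in a blinded fashion". The extension of that test also concerns stimulation: "A similar protocol will then be used to determine whether adaptive cortical stimulation can better control mood symptoms than continuous cortical stimulation".

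Section 9.0 compares time points, DBS on and off, and medication on and off within subjects. It lists three criteria that would justify a larger trial. The third is: "Therapeutic benefit in non-motor symptoms produced by cortical stimulation (open loop or closed loop) or neurofeedback training".

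**The concern.** Only one task condition is described: true feedback with an instruction to minimise. If the signal falls, voluntary control is one explanation. Habituation, fatigue, a medication effect still evolving within the session, and engagement with a visual task are others. Nothing in the plan tells them apart.

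The protocol itself expects such movement. Hypothesis 2 has prefrontal signals varying with medication state in patients with non-motor fluctuations, and section 3.0 says symptoms may fluctuate spontaneously. For stimulation, the sponsor uses sham and blinding "in order to prevent experimental biases arising from a participants' expectations". Neurofeedback patients know the goal and watch their apparent success while their symptoms are rated, but they have no such protection.

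Two things are at stake: what can be concluded on Hypothesis 4, and a decision rule. The third criterion is joined by an or, so an uncontrolled symptom change during neurofeedback could meet it with no contribution from stimulation.

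**Working it through.** **1. Which planned comparison could test neurofeedback?** Take the factors in section 9.0 and see which vary at visits 18-19 in Table 2.

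| Factor in section 9.0 | At visits 18-19 | Isolates regulation? |
|---|---|---|
| DBS on/off | Stimulation off | No, held fixed |
| Medication on/off | Medication on | No, held fixed |
| Time point | Varies | No, time also carries drift and habituation |

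No feedback or instruction factor is listed. The correlation of symptoms with physiology, also planned, does not supply one.

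**2. Does rest fill the gap?** In part. A same-session contrast of rest with cursor task could be computed, and it would remove some between-visit drift from the signal. It is not named as the neurofeedback comparator, its order is not specified, and it differs from the task in attention and visual input. It does nothing about expectation in symptom ratings.

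**3. Size of the problem (illustration only).** The plan states no alpha, power, effect size or SD, and no pre-post test for neurofeedback, so there is no figure of its own to reproduce. Assume n = 10, a two-sided 0.05 paired t-test, no specific effect of neurofeedback, and a non-specific mean shift of d SDs of change.

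P(significant improvement) = 1 − F(t*; 9 df, noncentrality d√10), with t* = 2.262.

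| d | d√10 | P, uncontrolled pre-post |
|---|---|---|
| 0 | 0 | 2.5% |
| 0.2 | 0.63 | 8% |
| 0.3 | 0.95 | 13% |
| 0.5 | 1.58 | 29% |
| 0.8 | 2.53 | 62% |

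Now add a within-subject control condition that carries the same shift. The contrast is (A + d) − (C + d) = A − C, so d drops out. With an assumed correlation of 0.5, the SD of the difference is √(1 + 1 − 2 × 0.5) = 1. Simulation (100,000 runs each at d = 0, 0.3, 0.5 and 0.8) gave 2.4% to 2.5% throughout. This holds only for shifts that both conditions share. Drift in the signal qualifies; expectation in ratings made under two visibly different tasks does not.

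**4. Block order.** Let the signal drift by b per block, with A = minimise-with-feedback and B = passive viewing.

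- Order ABBA: mean positions are (1 + 4)/2 = 2.5 and (2 + 3)/2 = 2.5, so drift contributes 0.
- Order ABAB: mean positions are (1 + 3)/2 = 2 and (2 + 4)/2 = 3, so drift contributes −b.

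A linear drift cancels exactly with balanced order, but only on average with simple randomisation.

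**5. What 10 patients can deliver.** A paired contrast has 80% power at about 1.0 SD of the difference. The 95% interval half-width is 2.262/√10 = 0.72 SD. That supports estimation rather than confirmation.

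**6. How many sessions?** The Synopsis (Study Design) puts training in phase 2, from 8 months to 5 years. Section 2.1 adds neurofeedback with Summit RC+S. Section 6.0 gives five visits between 13 and 24 months for closed-loop and neurofeedback work together. Table 2 names training only at visits 18-19. The amount of neurofeedback data is therefore not settled.

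**The case against.** The strongest reply is that this is a declared pilot of 10 patients. Section 9.0 says it is likely too small for definitive answers and calls the Nexus work exploratory. The criteria only justify a larger trial, where a controlled test could follow. Rest is recorded in the same sessions, medication and stimulation states are fixed at visits 18-19, and practice is part of what learning means.

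Much of this stands, and it rules out stronger statements that a reader might infer:

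- *That there is no comparison at all, or that Hypothesis 4 is unanswerable.* Rest data exist and carry some information.
- *That the plan counts any drift as learning.* No rule for learning is written down; the gap is an unspecified analysis.
- *That sessions start from a high signal, so regression to the mean is built in.* The section 6.0 text on recording symptomatic patients concerns testing stimulation strategies.
- *That exactly two visits are affected.* The documents disagree on the number.
- *That control blocks would also clean up the symptom ratings.* The patient can see which block is running, so expectation remains.

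The reply does not remove the core point. Rest is neither designated nor matched, and fixing the medication state does not prevent change within a session. A pilot used to justify a larger trial still needs an estimate that can be interpreted.

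**Conclusion.** The point holds in limited form: neurofeedback has no designated or matched comparator and no named contrast. As written, a fall in the signal cannot be attributed to voluntary control, and symptom change under open neurofeedback cannot be separated from drift, repeated assessment or expectation. Even so, neurofeedback alone can satisfy the third success criterion.

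The size cannot be derived from the documents. The 8% to 62% range rests on assumed shifts of 0.2 to 0.8 SD and on a pre-post test that the plan does not specify; it shows how sensitive an uncontrolled reading would be, not an error rate of this trial. The recording and stimulation aims are unaffected. This is an inexpensive improvement, not a fatal flaw.

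**What to change.** 1. Within the existing neurofeedback sessions, interleave minimise-with-feedback blocks with passive-viewing blocks (replayed cursor, no instruction to regulate). Use a balanced order such as ABBA, counterbalanced with BAAB across patients or sessions.
2. Pre-specify voluntary control as the within-session difference in the target signal between block types, and learning as the change in that difference across sessions. Report both as estimates with intervals. The difference reflects instruction and effort as well as feedback, so do not present it as the effect of feedback alone.
3. Treat VAS change in these blocks as descriptive. Label neurofeedback symptom benefit as feasibility only, and remove it as a stand-alone route to the third success criterion.
4. Reconcile the number and timing of neurofeedback sessions across the Synopsis, section 2.1, section 6.0 and Table 2.

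The cost is software set-up and fewer true-feedback trials per session, which matters more if there prove to be only two sessions. No extra visits or patients are needed. Item 3 is a text change and can be made even if the blocks are not adopted.

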## **7.0 Clinical Measurements**

### **Primary**

Physiological measurements related to neural oscillatory activity will include: power-spectral analysis studying multiple frequency bands (i.e. in the delta, theta, alpha, beta, gamma bands), cross-frequency coupling (22-24) and coherence between electrodes.

### **Secondary**

Clinical ratings of non-motor symptoms will be measured by multiple scales such as BDI-II, BAI, PAS, HADS, QUIP, YBOCS, VAS. Clinical rating scales of motor function will include NEW MDS UPDRS I-IV and dyskinesia rating scales. UPDRS part III will be scored on and off of antiparkinsonian medications. Additional measures will include Clinician Global Impression of Change (CGI-C) and Patient Global Impression of Change (PGI-C). Baseline comprehensive neuropsychological testing will be performed including: Montreal Cognitive Assessment (MoCA), the Columbia Suicide Severity Rating Scale (C-SSRS), Symbol-Digit Modality Test (SDMT, written and oral versions); Delis Kaplan Executive Function System (DKEFS Trail making test, Design Fluency), Neuropsychological Assessment Battery (NAB Digit Span, Memory, Visual Discrimination);

Rey-Osterreith Complex Figure (ROCF Copy & Immediate Trials); Controlled Oral Word Association (COWA, FAS & Animal Fluency), Boston Naming Test. Several of these tests (MoCA and Neuropsychological Assessment Battery) have alternative forms available which will be used to avoid practice effects.

All motor scales will be performed or administered by a movement disorders neurologist at baseline, 12 months and 24 months of DBS therapy. For all other visits a subset of these scales will be used based on patients symptoms and will be collected by members of the research and clinical teams.

## **8.0 Data Management**

All physiological data will be stored in password protected computers in the PI's laboratory that is always locked with a keyless card-access entry system. Data will be backed up on UCSF's HIPAA-compliant server. In publications or presentations of the data, data will be grouped by case number in chronological order with all patient identifiers removed. All DBS patients at our center routinely undergo videotaping and sign a separate consent to be videotaped. When presenting videotape data at scientific conferences, we will utilize only videos from patients who have consented to have their videos shown. With patient's permission, de-identified electrophysiological data may be shared with Medtronic or other researchers at other institutions, in accordance with HIPAA regulations.

Clinical data (baseline and follow up rating scales) will be entered into a customized, password-protected encrypted web-based database. This resides on a server at UCSF and is managed by the Department of Neurology, with backup support by the information technology service at UCSF. The database can be accessed by a licensed user from a secure internet server at UCSF but is protected by firewalls from networks outside of our institution.

## **9.0 Statistical Methods and Data Analysis**

LFP data will be analyzed using wide power-spectral analysis as well as analysis of specific frequency domains (i.e. in the delta, theta, alpha, beta, gamma bands). We will also examine region-specific coherence and cross-frequency coupling in addition to coherence between cortical and subcortical brain areas. Using a repeated measures ANOVA statistical analysis, summary statistics for power in relevant frequency bands, power changes, and magnitude of coupling and coherence will be compared at different time points, different DBS conditions (on and off), different medication states (on and off), in a repeated measures (within subjects) design. The small number of subjects is mitigated by the ability to study varying mood states longitudinally within each subject. We will assess the correlation between the severity of non-motor symptoms and brain physiology measures. Additionally, bootstrapping statistical applications (i.e. a Monte Carlo algorithm) and general linear mixed models can be utilized to investigate potential statistical effects, given the small sample size).

Since this is a pilot study of chronic cortical recording, the sample size is likely to be too small to provide definitive answers to all research questions. Based on this exploratory analysis, it is anticipated that the next phase of the study will focus on a subset of the research aims, with 10 subjects per group.

Sample size calculation: This is a pilot study of a novel chronic brain recording technique. The goals are to assess technique feasibility, to collect pilot data that will be used to frame more detailed hypothesis about DBS mechanisms, and (in the add-on study using Nexus-D and E) to explore potential strategies for therapeutic use of the Activa PC+S and Summit RC+S neural interface. Thus, there is no formal sample size calculation.

*Criteria for study success that would justify a larger subsequent trial:* This study will be considered to justify a larger subsequent trial if we can demonstrate:

- 1) Chronic LFP recording from the cortex, of adequate quality to assess signatures of non-motor symptoms
- 2) No permanent serious adverse events occur
- 3) Therapeutic benefit in non-motor symptoms produced by cortical stimulation (open loop or closed loop) or neurofeedback training.

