## **2.1 Study Objectives**

This study will allow us to both define the neural correlates of non-motor symptoms as well as to test the efficacy of stimulation in alleviating these symptoms. The Medtronic Activa PC+S device will allow us to monitor cortical and subcortical brain signals while non-motor symptoms of PD are assessed by subjective (i.e. patient reports and questionnaires) and objective measures (blood pressure, electrodermal activity, and/or task performance in tasks that probe emotional state). Using Nexus-D and E, we will then develop closed-loop paradigm using the physiological biomarker underlying non-motor symptoms, identified in the first phase of this study, to automatically adjust stimulation parameters. Finally, using Nexus-D we will train patients to voluntarily modulate their abnormal brain signals to reduce symptoms. Summit RC+S will allow us to implement the fully closed-loop deep brain stimulation paradigm and neurofeedback components.

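### Success criterion 3 claims symptom benefit caused by treatment, but it is not tied to the protocol's own blinded active-versus-sham test, and no analysis of the stimulation effect on symptoms is planned

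*Combined protocol and SAP*

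**What the plan says.** Section 9.0 lists three conditions that would justify a larger trial. The third is "Therapeutic benefit in non-motor symptoms produced by cortical stimulation (open loop or closed loop) or neurofeedback training". It names no comparator, measure or result that would satisfy it. Section 2.1 also states an aim "to test the efficacy of stimulation in alleviating these symptoms".

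The analysis text in Section 9.0 has three parts:
- a repeated measures ANOVA in which "summary statistics for power in relevant frequency bands, power changes, and magnitude of coupling and coherence will be compared at different time points", and also across DBS and medication states;
- one use of symptom scores: "We will assess the correlation between the severity of non-motor symptoms and brain physiology measures";
- bootstrapping and mixed models as an option, with no outcome or contrast attached.

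Section 6.0, in the text on stimulation states, describes a two-week test of active against sham cortical stimulation. The patient and the researchers who deal with the patient are blinded, "in order to prevent experimental biases arising from a participants' expectations". Table 2 lists a blind test at visits 16-17. It is optional: once promising settings are found, "patients might be offered to participate in a blind study of the effect of chronic cortical stimulation". Its symptom outcome is left open: "non-motor symptoms will be assessed with tablet-based VAS and/or performance of tablet-based cognitive/emotion tasks". The one analysis stated for it is of the stimulation effect on the biomarker.

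**The concern.** To say that benefit was produced by an intervention, one needs a comparison that separates it from expectation, drift and attention. The protocol contains such a comparison for stimulation, and introduces it for that reason, but the success criterion does not use it. As written, the criterion can be met from two weaker sources:
- the visit 7-10 sessions in Table 2, in the fixed order off, on, off, with no blinding described;
- neurofeedback training (Section 6.0, Nexus-D and E System Study), where symptoms are assessed while patients try to move a cursor and no control condition is described.

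At stake is the go/no-go claim. An expectation effect could be read as treatment benefit and carried into the case for a larger trial of an implanted cortical lead.

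**Working it through.** **1. What each source could support**

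| Source | Control | Blinding | Symptom analysis stated |
|---|---|---|---|
| Off-on-off, visits 7-10 | Stimulation off, fixed order | None described | None |
| Active versus sham, visits 16-17 | Sham, pseudorandom | Patient and the researchers in contact | None (biomarker only) |
| Adaptive versus continuous | Continuous stimulation; sham not explicit | Similar protocol to the above | None |
| Neurofeedback | None described | None described | None |

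Only the second row is a sham-controlled, blinded contrast on symptoms.

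**2. Size of the expectation problem.** The documents state no test, alpha, effect size or SD, so there is no figure to reproduce. From the documents: n = 10. Assumed: no true effect; one pre-named measure; benefit declared if a one-sample t test on patient-level differences is significant at one-sided 0.025; expectation shift d in SDs of those differences.

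With drift b per period and shift s, the off-on-off contrast is on minus the mean of the two off periods: (b + s) − (0 + 2b)/2 = s. Linear drift cancels; expectation does not.

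P(false benefit) = P(T > 2.262), where T is noncentral t with 9 df and noncentrality d√10:
- d = 0: 0.025
- d = 0.2: noncentrality 0.632, probability 0.082
- d = 0.5: noncentrality 1.581, probability 0.293

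Simulation with linear drift of 0 or 0.5 per period agrees to within simulation error. An uncontrolled before-after neurofeedback comparison gives the same values for any non-specific shift of that size.

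**3. How far blinding protects.** Patients operate the test themselves: "participant will be asked to activate one of these 2 groups for 1h in a pseudorandom fashion". Recognising one group reveals the other. Simulating 10 patients, with a 0.5 SD shift only in those who recognise the active group:

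| Share recognising | 0% | 25% | 50% | 100% |
|---|---|---|---|---|
| False benefit | 0.025 | 0.053 | 0.101 | 0.292 |

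**4. Precision of the blinded contrast.** The half-width of the 95% interval is about t(0.975, n−1)/√n SDs of patient-level differences:
- n = 10: 2.262/3.162 = 0.72
- n = 8: 2.365/2.828 = 0.84
- n = 5: 2.776/2.236 = 1.24

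If the interval had to exclude zero, power at a true 0.8 SD would be 62%, 50% and 28% for 10, 8 and 5 entrants.

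**5. Why the model needs two details.** Using 1.96 in place of the t limit raises one-sided error from 0.025 to 0.041 (n = 10) or 0.061 (n = 5). Omitting a patient-by-condition term, when the true effect varies between patients by 0.3 or 0.5 day-to-day SDs, gives about 0.04 or 0.07 (n = 10, assuming 7 active and 7 sham independent days).

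**The case against.** The strongest reply is that this is a pilot. Section 9.0 says that the sample is probably too small for definitive answers and that there is no formal sample size calculation. That stands, and it rules out a stricter remedy. A reader might infer that the criterion should require an interval excluding zero, or a minimum number of entrants. In a study of this size a useful treatment would often miss such a rule (step 4), and the documents give no basis for one.

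Other readings that go too far:
- **That no analysis of the blinded test exists.** Section 6.0 plans one for the biomarker. The gap is for symptoms.
- **That the protocol names no symptom measures.** The synopsis and Section 7.0 list several, give VAS the role of rating symptoms at the time of recording, and the synopsis adds possible objective measures. What is missing is a choice among them for this criterion.
- **That closed-loop results should be barred from the criterion.** Closed-loop stimulation is a stated aim; excluding it would rewrite the study's purpose.
- **That 8% or 29% is this trial's error rate.** The plan sets no decision rule, so these figures only show scale. The blinded test's advantage disappears if every patient recognises the active group.

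It is also fair to say that a listing in Table 2 does not make the test mandatory, and that the text leaves its daily schedule unclear. Neither removes the point: the criterion makes a causal claim and does not use the comparison designed to support it.

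**Conclusion.** The concern holds in this form: criterion 3 makes a causal claim about symptoms, is not linked to the blinded active-versus-sham test, and has no planned analysis of the stimulation effect on symptoms. Under the stated assumptions, a modest expectation shift (0.2 to 0.5 SD) would produce apparent benefit in 8% to 29% of null studies judged on unblinded sessions, against 2.5% with intact blinding and 5% to 10% if a quarter to a half of patients recognise the active group. The shifts, recognition shares and 0.025 level are assumptions. The textual gap does not depend on them. This is a cheap improvement to the go/no-go claim, not a fault in the study's power or its exploratory purpose.

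**What to change.** In Section 9.0, state that for cortical stimulation criterion 3 is judged primarily on the blinded active-minus-sham contrast of Section 6.0:
- **Outcome:** one VAS per patient, for a qualifying symptom, named before that patient's test, with its direction of scoring stated.
- **Analysis:** one mixed model with a patient intercept, a patient-by-condition random effect and small-sample degrees of freedom (Kenward-Roger or Satterthwaite). Report the estimate and its 95% interval, without requiring it to exclude zero.
- **Schedule:** state in Section 6.0 whether one or both conditions run each day, and the active-to-sham balance, so that the contrast can be analysed.
- **Entry:** offer the test to every patient who meets its existing entry condition; participation stays voluntary. Report how many of all implanted patients met the condition, entered and completed.
- **Blinding check:** at the end, ask each patient which group they think was active, and report the answers.
- **Other results:** report off-on-off, adaptive-versus-continuous and neurofeedback findings as supportive. Do not attribute benefit causally to neurofeedback without a control condition.

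The cost is protocol wording and an IRB amendment. The estimate will be imprecise if few patients enter, and its protection depends on intact blinding. It will apply only to patients with promising settings and to one hour of stimulation a day.
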